**B. Sample Size.**

- i. Total number of subjects who will be approached (including screen failures, controls and subject withdrawals) to reach enrollment numbers for the lifetime of the study at this investigator's sites.

140 households

- ii. Total number of subjects who will be enrolled in the study at this investigator's site.

This study will enroll 100 households without a konzo individual (based on neurological exam) in the family and where the mother of one of more children under 4 yrs of age is the principal food preparer.

- iii. Describe the statistical justification or rationale for the proposed sample size. Considerations for sample size may include the acceptable level of significance, power of the study, expected effect size, underlying event rate in the population, standard deviation in the population, saturation of themes, and/or have a theoretical basis.

This exploratory developmental R21 project aims to generate hypotheses for subsequent formal testing in an R01-supported larger trial. Therefore present sample size considerations are based

on project timeline and resources. With n=66 in MISC+WTM arm and n=34 in WTM only arm. Based on our clinical studies with a biweekly MISC caregiver training with mothers with HIV in rural eastern Uganda, we expect an over 90% retention rate for the full year. With this retention rate, the unadjusted effect size of 0.60 is detectable as statistically significant with power of 0.80 and 0.05 level of significance in two-tailed tests, that is differences between trial arms of 0.6 of the standard deviation or greater will be captured with statistical significance. For the main trial arm effect (differences between arms over time) from two repeated measures at 6 and 12 months with the planned covariance adjustment for baseline, the adjusted standard deviation is smaller than the unadjusted due to the reduction in error variance. Assuming correlation of 0.4 between pairs of repeated measures seen in past testing of MISC, the adjusted detectable effect size is 0.44. This effect size is consistent with past testing of MISC in HIV-affected households that produced effect sizes ranging from 0.35 to 0.53, and is below the threshold of 1/2 of the standard deviation for clinical significance. Thus any meaningful differences between arms will be captured with the proposed sample size. If the differences between trial arms correspond to the adjusted effect size smaller than 0.44, the effect size will be estimated in this study and used to power future clinical trial studies.

**10. Minimal Risk Research.** Complete the following question if you selected an expedited category in Question 8A.

- A.** Briefly describe the background for conducting the research. (1-2 sentences)

- B.** Sample Size.

- i. Provide an estimated sample size for the lifetime of the study at this investigator's sites.

- ii. Describe the basis for that estimate.

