### B. Describe how subjects will be identified and recruited, including who will perform the recruitment.

This study will enroll 100 households where the mother is the principal caregiver and food preparer for one or more children from 1 to 4 yrs of age. If multiple biological children for a study mother are in that age range, they will all be enrolled and assigned as a household to the same caregiver training trial arm (either MISC/WTM or WTM only). However, the mother cannot be diagnosed with konzo following a full neurological exam at study enrollment, so that she is able to fully implement MISC and/or WTM training. Randomization occurs by geographic location (i.e. village) rather than individually to minimize the likelihood of contamination and diffusion effects within a community. Our MISC biweekly year-long caregiver training with rural Ugandan HIV mothers using MISC training resulted in a pre- to post-year retention rate of over 90% in our dyads, and we anticipate at least that retention rate given the fact that our mothers and children are not affected by HIV and those health and motivational issues.

We will randomly select our eligible households from a health zone census already established by the PRONANUT for Kahemba district in preparation for the R01 peer- versus professional-led non-inferiority clinical trial for teaching small groups of mothers the use of WTM to detoxify their cassava flour before eating. The present study will stratify its sample selection so that half of the participating households will be from peer- and half will be from professional-led health zones. Ho Also, the mothers of the study children are responsible day-to-day for cassava flour preparation. Mother and child have no prior history of severe medical condition or brain infection, accident, or injury which may preclude the ability to learn WTM and/or MISC and benefit from it in terms of functionality (maternal) or neurodevelopmental (child) outcomes. Once enrolled, they will be

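### The stated detectable effects of 0.60 and 0.44 do not follow from 66 vs 34 households at 90% retention, which gives about 0.63 and 0.46

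*Combined protocol and SAP*

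**What the plan says.** All of the power reasoning is in section 9.B.iii of the combined protocol and SAP.

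- Arms: "With n=66 in MISC+WTM arm and n=34 in WTM only arm".
- Retention: "we expect an over 90% retention rate for the full year". Section 12.B, on recruitment, refers to the same Ugandan experience and adds that "we anticipate at least that retention rate given the fact that our mothers and children are not affected by HIV".
- Unadjusted claim: "With this retention rate, the unadjusted effect size of 0.60 is detectable as statistically significant with power of 0.80", with "0.05 level of significance in two-tailed tests". The paragraph restates it: "differences between trial arms of 0.6 of the standard deviation or greater will be captured with statistical significance".
- Adjusted claim: with measures at 6 and 12 months, adjustment for baseline, and a correlation of 0.4 between pairs of measures, "the adjusted detectable effect size is 0.44". The paragraph's last sentence uses this figure again as a cut-off: "If the differences between trial arms correspond to the adjusted effect size smaller than 0.44".

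The section also says that the study is exploratory and that its size was set by timeline and resources. It compares 0.44 with effects of 0.35 to 0.53 in earlier MISC work and with a clinical threshold of half a standard deviation. It does not give the number of completers assumed, or say whether a t or a normal calculation was used.

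**The concern.** The wording ties 0.60 to three things at once: the 66:34 split, the expected attrition and 80% power. An unequal split and a loss of up to a tenth of the households both raise the smallest detectable effect. A figure that allows for both should therefore be visibly larger than one for 66 vs 34 with everyone followed.

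This is the only power statement in the documents. The paragraph uses it to conclude that any meaningful difference will be captured, and it uses 0.44 as the line below which the effect will only be estimated. If the figures belong to a different design, the paragraph credits this trial with somewhat more power than its own inputs give.

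**Working it through.** **Inputs (section 9.B.iii).** Arms 66 and 34; retention taken as 90%, the only number given; two-sided 0.05; power 0.80; two follow-up measures with baseline adjustment; correlation 0.4. Households are treated as independent, one unit each, because the paragraph mentions no other allowance.

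**Formulas.**

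- Unadjusted, normal approximation: d = (1.960 + 0.842) × √(1/n₁ + 1/n₂) = 2.802 × √(1/n₁ + 1/n₂). The t version solves for the d at which the noncentral t test with n₁ + n₂ − 2 degrees of freedom has power 0.80.
- Adjusted: multiply by √((1 + ρ)/2 − ρ²). This is the residual SD of the mean of two follow-up measures after adjusting for one baseline, with every pairwise correlation equal to ρ. With ρ = 0.4 it is √(0.70 − 0.16) = √0.54 = 0.735.

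**Step 1: check the plan's adjustment.** 0.60 × 0.735 = 0.441, which rounds to the stated 0.44. The adjustment step is sound, so any fault in 0.44 comes from 0.60.

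**Step 2: find a design that gives 0.60.** For 66 vs 34 with no dropout, √(1/66 + 1/34) = 0.2111, so d = 2.802 × 0.2111 = 0.591 (normal) or 0.597 (t). For 45 vs 45, √(2/45) = 0.2108, with almost the same result.

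**Step 3: use the stated design.** 0.9 × 66 = 59.4 and 0.9 × 34 = 30.6. √(1/59.4 + 1/30.6) = 0.2225, so d = 2.802 × 0.2225 = 0.623 (normal) or 0.630 (t). Adjusted: 0.623 × 0.735 = 0.458, or 0.630 × 0.735 = 0.463.

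| Households analysed | Unadjusted, t (normal) | Adjusted, t (normal) |
|---|---|---|
| Stated in the plan | 0.60 | 0.44 |
| 66 / 34, no dropout | 0.597 (0.591) | 0.439 (0.435) |
| 45 / 45 | 0.597 (0.591) | 0.439 (0.434) |
| 62.7 / 32.3, 95% retained | 0.613 (0.607) | 0.451 (0.446) |
| 59.4 / 30.6, 90% retained | 0.630 (0.623) | 0.463 (0.458) |
| 59 / 31, whole numbers | 0.628 (0.622) | 0.462 (0.457) |

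**Step 4: rule out other readings.** One-sided testing at 90% retention gives 0.553 (normal) or 0.558 (t), so it does not explain 0.60. Whole-number splits of 60/31, 59/31, 60/30 and 59/30 give 0.620 to 0.635 across both methods.

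**Step 5: retention needed.** The unadjusted figure falls to 0.605, and so rounds to 0.60, at 97.5% retention (t) or 95.6% (normal). The adjusted figure falls to 0.445 at 97.3% or 95.4%.

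**Step 6: size in power and households.** At 59.4 vs 30.6, power is 0.760 (t) or 0.769 (normal) for an unadjusted 0.60, and 0.758 or 0.768 for an adjusted 0.44. Power for an adjusted 0.5 SD is 0.86 (t), against 0.89 with complete follow-up. For scale, 0.60 at 90% retention and a 66:34 split corresponds to about 110 enrolled households (t) or 108 (normal), rather than 100.

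**The case against.** The strongest objection is that 90% is a floor. The plan expects more than 90%, and section 12.B expects at least as much again. At 95% the unadjusted figure is 0.607 to 0.613 and power at 0.60 is 0.78 to 0.79; at 97% the normal approximation gives 0.600. This stands as a limit on the size of the discrepancy. It does not remove it: no higher rate is given, a reader would not infer 96% to 98% from the wording, and a detectable effect quoted against a floor should hold at that floor.

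Second, the adjusted figure uses a 6-month measure, and households lost later may still contribute it. Suppose everyone is seen at 6 months and 90% at 12, with a constant effect. The information per enrolled household is then 0.90/0.54 + 0.10/0.84 = 1.786, where 0.84 = 1 − 0.4². The adjusted figure becomes 0.591 × √(1/1.786) = 0.443 (normal) or 0.447 (t). With 95% seen at 6 months it is 0.450 or 0.455. So 0.46 assumes that dropouts contribute to neither visit. The documents do not say how partial data are handled, and this reading does not rescue the unadjusted 0.60.

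Third, all of a mother's children in the age range are enrolled, so child outcomes may have more than one observation per household. As illustration only, 1.2 children per household with a within-household correlation of 0.5 gives 0.597 (normal) or 0.603 (t) at 90% retention. Neither number is in the documents, nothing in the paragraph suggests such a calculation, and it cannot apply to caregiver outcomes.

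Finally, little depends on the difference in an exploratory study sized by resources. That is right, and it is why the point is minor.

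**Conclusion.** The concern holds. For 66 vs 34 at 90% retention the detectable effects are about 0.63 unadjusted (0.62 by the normal approximation) and 0.46 adjusted. The plan understates them by about 0.03 and 0.02 SD, and power at its stated effects is about 0.76 to 0.77. By the t-test, the printed figures match complete follow-up of 66 vs 34, and equally 90 completers in equal arms. The documents do not show whether the attrition or the unequal allocation was left out.

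This rests on retention at the 90% floor, one independent unit per household, and dropouts missing from both follow-up visits. On that basis 0.46 is still below 0.5 SD and within 0.35 to 0.53, so the paragraph's own comparisons survive. The arithmetic is firm and the consequence is minor. Randomisation by village is a separate matter; allowing for it would raise all of these figures, and nothing here depends on it.

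**What to change.** In section 9.B.iii, do one of two things:

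- restate the detectable effects as 0.63 and 0.46 at 90% retention (about 59 vs 31 households); or
- keep 0.60 and 0.44 and say that they assume complete follow-up of 66 vs 34.

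Carry the choice through to the two places where the paragraph repeats the figures: the restatement as a fraction of the standard deviation, and the closing sentence that uses 0.44 as a cut-off. State the retention rate, the allocation and the method (t or normal). Add that the figures treat households as independent, so that the new numbers are not read as allowing for village randomisation.

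The cost is a change of wording at four places in one paragraph. Enrolment, design and analysis are unaffected.

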### **3. Subject Population.**

#### **A. Describe the subject population.**

We will study 100 non-konzo mother/child dyads, and all household children 12 to 48 months of age. 34 mother/child pairs will receive 12-months of biweekly home-based personalized training sessions with wetting method (WTM) training only to detoxify cassava flour in the prevention of konzo, and 66 dyads will receive 12 months of MISC caregiver training to improve early childhood development (ECD) combined with WTM. These families represent a homogenous population of Congolese people living in the Kahemba district of the Bandundu Province, Democratic Republic of Congo (DRC) in southwestern Bandundu province. People in this rural district depend heavily on daily cassava root and leaves for food and cash income. A typical population of 100,000 cultivates about 5000 hectares of cassava per year. Traditional varieties of cassava, which are subject to the cassava mosaic virus, yield around 6 tons/hectare per year. Crop losses in the 1990s ranged from 5% to 95%, thereby resulting in severe food insecurity. Cassava dependency resulted in up to 5% of individuals in affected villages developing walking difficulties typical of konzo. A substantially larger percentage (estimated up to 10%) has neurological signs and symptoms of an earlier stage of konzo in which ambulatory difficulty is not overt. Our recent findings suggest that deficits in cognition may also be part of neurological picture. Therefore, this is an at-risk population.

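### Baseline score is the only covariate the plan states; adding child age and sex to the child-outcome models is a nearly free gain for any score that is not age-standardised

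*Combined protocol and SAP*

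**What the plan says.** The only description of the analysis model is in the sample-size justification (Section 9.B.iii). The main arm effect is to be estimated "from two repeated measures at 6 and 12 months", "with the planned covariance adjustment for baseline". The inputs are stated as "With n=66 in MISC+WTM arm and n=34 in WTM only arm", "the unadjusted effect size of 0.60 is detectable as statistically significant", and "Assuming correlation of 0.4 between pairs of repeated measures seen in past testing of MISC". From these the section arrives at an adjusted detectable effect of 0.44.

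Section 3.A enrols "all household children 12 to 48 months of age". Section 12.B allocates by village, keeps siblings in one arm, and stratifies sample selection by peer-led versus professional-led health zone. Child age and sex appear nowhere as a covariate, stratum or balancing factor. The documents do not give the number of villages. They also do not say whether the Mullen, Fagan, vigilance (ECVT) or COAT scores will be analysed raw or age-standardised.

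**The concern.** Children at the top of the age range are four times as old as those at the bottom, and the child outcomes are developmental tests. Unless a score is age-standardised, age is an obvious candidate to explain variation in it. Age has to be known for every child because it is an eligibility criterion. The stated model uses it only indirectly, through the baseline score, and the plan puts the correlation between repeated measures at only 0.4.

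Two things are at stake for the child outcomes:

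- **Precision.** Section 9.B.iii cites past MISC effects of 0.35 to 0.53. The detectable effect of 0.44 is the midpoint of that range, so a modest gain would matter.
- **Chance imbalance.** Nothing in the village allocation balances age. The same section says that an effect smaller than 0.44 will be estimated and used to power later trials, so a distorted estimate would carry forward.

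**Working it through.** **1. Reproduce the plan's figure.** For the mean of two follow-up measures adjusted for one baseline, with common correlation ρ, the variance factor is (1+ρ)/2 − ρ². With ρ = 0.4 this is 0.70 − 0.16 = 0.54. Then 0.60 × √0.54 = 0.441, which is the stated 0.44. The figure follows from baseline adjustment alone, so the calculation takes no credit for age or sex. (The 0.60 itself matches all 100 households: 0.591 by the normal formula, 0.597 by the t-test. At exactly 90% retention it would be 0.623. That is a separate matter; the plan's 0.60 is kept here.)

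**2. What baseline adjustment does to an age effect.** Let r be the correlation of the score with age, assumed equal at every visit, and let d be the arm difference in mean age in SD units. The unadjusted bias is r·d. Baseline adjustment with slope 0.4 subtracts 0.4·r·d and leaves 0.6·r·d. So 40% is removed and 60% remains.

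**3. Precision gained by adding age.** After baseline adjustment, age and the mean follow-up score have covariance r − 0.4r = 0.6r, and age has remaining variance 1 − r². Age therefore explains a share (0.6r)² / [0.54(1 − r²)] of the remaining variance. The detectable effect becomes 0.441 × √(1 − share). The documents give no r, so these values are assumptions:

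| Assumed r | Share of remaining variance | Detectable effect |
|---|---|---|
| 0 (age-standardised) | 0 | 0.44 |
| 0.20 | 0.0144 / 0.5184 = 3% | 0.43 |
| 0.36 | 0.0467 / 0.4700 = 10% | 0.42 |
| 0.48 | 0.0829 / 0.4156 = 20% | 0.39 |
| 0.56 | 0.1129 / 0.3707 = 30% | 0.37 |

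These figures make no allowance for village clustering, as the plan's 0.44 does not.

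**4. Size of a chance age imbalance.** Assume ages uniform over 12 to 48 months, so the SD is 36/√12 = 10.4 months. Assume also one child per household and no clustering of age by village. The SD of the arm difference in mean age is 10.4 × √(1/66 + 1/34) = 10.4 × 0.211 = 2.2 months. Bias left after baseline adjustment, in outcome SDs:

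| Assumed r | 1-SD imbalance (2.2 months): 0.6 × r × 0.211 | 6-month imbalance: 0.6 × r × 0.577 |
|---|---|---|
| 0.2 | 0.03 | 0.07 |
| 0.4 | 0.05 | 0.14 |
| 0.6 | 0.08 | 0.21 |

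Under these assumptions a 6-month difference is a 2.7-SD event (6/2.2). It would be less remote if child age clustered by village, on which the documents are silent.

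**The case against.** The strongest reply is that the baseline phrase explains why 0.44 is smaller than 0.60; it is not a model specification. A reader might infer that the plan has decided to adjust for baseline alone. The documents do not support that: nothing limits the adjustment to baseline, and no full model is given. What stands is narrower: baseline is the only adjustment stated.

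Three other stronger readings also fail.

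- **Age imbalance is likely and left uncorrected.** The number of villages is not given, and few villages produce large age differences only if age clusters by village. Households are to be drawn at random from a census. Without such clustering a typical imbalance leaves 0.03 to 0.08 SD, and baseline adjustment has already removed part of it.
- **The gain is known to be 10% to 30%, worth 11% to 43% more households (1/0.9 to 1/0.7).** No age-outcome correlation is documented, and reaching 30% needs r of about 0.56. Age alone would then supply 0.31 of the 0.40 repeat correlation, over three quarters. The household equivalent also treats households as independent, whereas villages are randomised and individual covariates mainly reduce within-village variance.
- **The main model as a whole is affected.** Aim 2 also covers household flour and caregiver mental health, where the child-age argument does not apply.

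The documents give no evidence of a sex effect either; age carries the argument. It is also fair to say that the trial is exploratory and sized by timeline and resources. That limits the consequences but does not make pre-specification less useful, because the effect estimates are meant to inform later trials.

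**Conclusion.** The point holds as an inexpensive improvement to the child-outcome analyses, not as an error in the plan's arithmetic. The 0.44 is correctly derived from its inputs, and leaving age out does not invalidate it; adding a prognostic covariate would keep or lower it.

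The size depends on scoring that the documents do not describe. For age-standardised scores the gain is near zero. For scores that are not, the detectable effect falls to between about 0.43 and 0.37 over assumed age-outcome correlations of 0.2 to 0.56. These figures rest on a constant age correlation across visits, the plan's 0.4 between measures, and no village clustering. Protection against imbalance is usually modest, but it is worth more if villages happen to differ in child age.

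**What to change.** For each child outcome, pre-specify a model with the baseline score, continuous child age at baseline and sex as covariates. State for each test whether raw or age-standardised scores are analysed. Caregiver and flour outcomes need no change on this account.

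The cost is a sentence or two in the analysis plan and one or two degrees of freedom. Age is already needed for eligibility. Sex should come with the demographic data in the questionnaire (Section 2), though it is not named there and this should be confirmed. Where scores are already age-standardised there will be little or no gain.

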**1. Hypothesis / Objective / Goals / Aims.**

Briefly describe the study's hypothesis / objectives / goals / aims.

Konzo is a neurological disease associated with chronic reliance on poorly processed cyanogenic cassava as the main source of food. We found that school age children from konzo areas present with poor neurocognition compared to those from nearby non-konzo areas, persisting and worsening even 4 years after initial assessment. Our most recent work has extended these findings to children as young as a year in age, suggesting that the neurodevelopmental impact from cassava cyanide neurotoxicity may begin as soon as children are weaned from breast milk to cassava porridge. The “wetting method (WTM)” is a simple and effective method of detoxifying cassava flour prior to eating that is being taught to rural women in a clinical-trial study by our group in the Democratic Republic of Congo (DRC). The present proposal seeks to combine a curriculum of mediational intervention for sensitizing caregivers (MISC) with a WTM training program (MISC/WTM). MISC is an early childhood development (ECD) caregiver training program previously demonstrated in clinical trials by [name] and colleagues to improve health, neurodevelopmental, and caregiver mental health outcomes in rural Ugandan HIV-affected households. Training 66 randomly selected moms from a cohort of 100 on MISC/WTM (while the remaining 34 get WTM only) will better sensitize mothers to their children’s development, leading to better WTM adherence while providing practical ECD benefits.

The Aims for this study are:

1. To establish the feasibility of adding a biweekly 1-year MISC/WTM training program for mothers and their 1 through 4-year-old children, led by peer trainers from the community. MISC has been previously implemented for HIV-affected households in Uganda, but not for konzo communities in the DRC.

2. To document whether better adherence to WTM through MISC will lead to lower household flour cassava cyanogenic content and lower urinary thiocyanate (U-SCN) levels in the mother/child dyads. We will also test for improved child outcomes on the Fagan Test of Infant Intelligence (with automated eye tracking), Mullen Scales of Learning (MSEL), the Early Childhood Test of attention (ECVT; eye tracking), and the Color-Object Association Test (COAT). Caregiver depression/anxiety and corresponding functionality for activities of daily caregiving should also significantly improve.

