## 2. Procedures.

Describe the research procedures that involve obtaining information or biospecimens about a living person through interaction or intervention and/or by obtaining their identifiable private information or identifiable biospecimens. If subjects will participate in or undergo an intervention, fully describe the intervention. If the procedures are longer than 1 page, provide a summary and include the full procedures as an attachment.

Caregiver/child dyads will be randomized (by cluster) whereby 66 of the 100 households will be selected to randomly receive MISC/WTM caregiver training to enhance caregiver mental health and functionality and early childhood development. The remaining 34 households will receive WTM only (considered the recommended standard of care for the prevention of konzo disease in at risk communities). This is in order to see if adding MISC to caregiver training enhances adherence to WTM for flour detoxification, corresponding child neurodevelopmental and caregiver functionality mental health outcomes – as compared to WTM alone for similar households. To maintain concealment of MISC training allocation, the randomization sequence was generated by the trial biostatistician located in the USA, who also serves as our clinical methodologist and biostatistician for the R01 WTM konzo prevention non-inferiority clinical trial.

The WTM intervention. The intervention will implement the WTM cassava processing technique in participating households. Twenty women with leadership and communication skills have already been trained and are implementing WTM in the R01 trial and will do the training for our WTM-only households in this R21 study. These are mothers who master the WTM technique and have been certified as trainers to train and support other small groups of other mothers. They have to be able to bring the cassava cyanogenic content to the lowest achievable level, which must be < 10 ppm as per the WHO recommendations.

The wetting method to remove cyanogens from cassava flour involves adding dry flour to a bowl and marking the level on the inside of the bowl. Water is then added with mixing, the volume of

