## 12. Screening, Recruitment, and Determining Eligibility.

### A. Describe the criteria for who will be included or excluded from the study, including how subjects will be screened for eligibility

The proposed study will enroll 100 households from villages not presently enrolled in the R01 study. Eligible households must have at least one child less than 4 years of age, and the biological mother of the child must be the primary caregiver and food provider for the child. Eligible households may NOT have an older child or other family member already affected by konzo, thus the results will be generalizable to a broader population. Enrollment and randomization will occur at the village level. After 100 households with children 1-4 years of age complete baseline assessments, 66 of them will be randomly selected to undergo individualized MISC+WTM training sessions by peers trained in the MISC+WTM curriculum, who will come to their homes for a 1 to 2 hr. session on a biweekly basis.

**Exclusion Criteria.** At pre- study medical examination we will exclude children with a medical history of serious birth complications, severe malnutrition, bacterial meningitis, encephalitis, cerebral malaria, or other known brain injury or disorder requiring hospitalization. Also children with seizure or other neurological disability will be excluded. Serious CNS neurodisabilities would prevent such children from completing the MISC intervention, and possibly significant portions of the neuropsychological test battery.

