## HRP-503 - Template – Protocol

cluster randomized to either the MISC/WTM or WTM-only peer-led training standard of care. Randomization will occur by geographic location (i.e. village) rather than individually to minimize the likelihood of “spillover” (contamination and diffusion) effects within a community, whereby caregivers receiving training by a specialist provider might share aspects of their experience with caregivers receiving training from a peer-provider. Therefore villages participating in this study will be randomly assigned to peer- versus specialist-led group training intervention (randomized cluster technique). To maintain concealment of allocation, the randomization sequence will be generated by the trial biostatistician who is a full professor at MSU and very experienced at the clinical methodology and the statistical assessment of our study outcomes. She is the clinical methodologist and biostatistician for the konzo WTM non-inferiority R01 study, and will serve the same role in this study. Child neurodevelopmental and urinary thiocyanate and quality of home environment and evaluation of observed MISC interactions using the caregiving videos will be done by research assistants blinded to caregiver training intervention arm in the present study.

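### Villages are randomised, but the 80% power at 0.60 and 0.44 SD makes no allowance for clustering, so the claim that meaningful differences will be captured is unsupported

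*Combined protocol and SAP*

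**What the plan says.** **Unit of randomisation.** Section 12.A says "Enrollment and randomization will occur at the village level". Section 12.B says "Randomization occurs by geographic location (i.e. village) rather than individually to minimize the likelihood of contamination and diffusion effects within a community", and its closing text has enrolled households "cluster randomized to either the MISC/WTM or WTM-only peer-led training standard of care". Section 2 also describes allocation by cluster.

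**Wording that points the other way.** Section 12.A continues that, once 100 households have completed baseline, "66 of them will be randomly selected to undergo individualized MISC+WTM training sessions by peers trained in the MISC+WTM curriculum". Section 1 likewise speaks of 66 mothers chosen at random from 100. Section 12.B also has a sentence assigning villages to peer-led versus specialist-led training, which is not the contrast this trial tests.

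**Power.** Section 9.B.iii takes 66 vs 34 households and expects more than 90% retention. It states: "With this retention rate, the unadjusted effect size of 0.60 is detectable as statistically significant with power of 0.80 and 0.05 level of significance". With two follow-up measures, baseline adjustment and a correlation of 0.4, the detectable effect becomes 0.44 SD. Because this lies below a 0.5 SD threshold for clinical significance, the section concludes: "Thus any meaningful differences between arms will be captured with the proposed sample size". It also calls the project exploratory, says its size rests on timeline and resources, and says that effects below 0.44 will be estimated for planning later trials.

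The documents give no number of villages, village size, ICC, design effect or analysis term for village.

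**The concern.** When villages are allocated, households in the same village share whatever is common to that village, and the arm comparison has only as many independent units as there are villages. Two things follow. The variance of the arm difference rises by roughly 1 + (m − 1) × ICC, with m households per village, and the reference distribution has about (villages − 2) degrees of freedom rather than 98. The only variance adjustment in Section 9.B.iii is the reduction for baseline.

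The final sentence depends on 0.44 being below 0.5 SD. If clustering moves the detectable effect above 0.5 SD, the argument fails by the plan's own standard, and a null result could be misread as evidence against a 0.5 SD effect. The estimates are also meant to size a later trial, which needs intervals and an ICC that reflect the clustering.

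**Working it through.** **Inputs from Section 9.B.iii:** 66 vs 34 households, two-sided 0.05, power 0.80, correlation ρ = 0.4, two follow-ups with baseline adjustment, threshold 0.5 SD. **Assumed, because not stated:** number of villages and ICC. The ICC here is that of the baseline-adjusted mean of the 6- and 12-month values. All powers use the noncentral t distribution.

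**1. Reproduce the plan's figures with independent households.**
- Standard error of the difference in SD units: √(1/66 + 1/34) = 0.2111. On 98 df the detectable effect is **0.597** (plan: 0.60).
- Variance factor for the baseline-adjusted mean of two follow-ups: (1 + 0.4)/2 − 0.4² = 0.54. Then 0.597 × √0.54 = **0.439** (plan: 0.44).
- Power is 0.804 at 0.60 and 0.802 at 0.44.
- An equal split of 90 retained households (45 vs 45) gives the same 0.597 and 0.439, so the exact basis is not known. On either basis the design effect is 1.

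**2. Room for clustering.** Power at the stated effects is already at 0.80, so there is no margin there beyond rounding. At 0.5 SD the margin is a design effect of (0.50/0.439)² ≈ 1.30 on 98 df, before any loss of degrees of freedom.

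**3. Illustrative village layouts.** All 100 households are analysed, with village sizes nearly equal within arm. For an arm of N households in villages of size m_j:

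variance = 0.54 × [(1 − ICC)/N + ICC × Σm_j²/N²], summed over arms; df = villages − 2.

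One cell in full, 7 vs 3 villages at ICC 0.05: sizes 10, 10, 10, 9, 9, 9, 9 give Σm² = 624, and sizes 12, 11, 11 give Σm² = 386.
- Variance = 0.54 × [0.95/66 + 0.05 × 624/66² + 0.95/34 + 0.05 × 386/34²] = 0.54 × 0.0662 = 0.0357, so SE = 0.189.
- At 0.5 SD the noncentrality is 0.50/0.189 = 2.64. On 8 df, power is 0.64.

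Adjusted effect detectable with 80% power (design effect alone, on 98 df, in brackets):

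| Villages | ICC 0 | 0.01 | 0.05 | 0.10 |
|---|---|---|---|---|
| 10 (7 vs 3) | 0.497 (0.439) | 0.520 (0.460) | 0.605 (0.535) | 0.697 (0.616) |
| 20 (13 vs 7) | 0.460 (0.439) | 0.469 (0.448) | 0.503 (0.480) | 0.543 (0.518) |
| 50 (33 vs 17) | 0.444 (0.439) | 0.446 (0.441) | 0.454 (0.450) | 0.465 (0.460) |

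Power on villages − 2 df:

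| Villages | Effect | ICC 0 | 0.01 | 0.05 | 0.10 |
|---|---|---|---|---|---|
| 10 | 0.44 | 0.70 | 0.66 | 0.53 | 0.43 |
| 10 | 0.50 | 0.81 | 0.77 | 0.64 | 0.52 |
| 20 | 0.44 | 0.77 | 0.75 | 0.69 | 0.62 |
| 20 | 0.50 | 0.86 | 0.85 | 0.80 | 0.73 |
| 50 | 0.44 | 0.79 | 0.79 | 0.77 | 0.76 |
| 50 | 0.50 | 0.89 | 0.88 | 0.87 | 0.85 |

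A simulation with an unweighted t test on village means (40,000 runs) gives power at 0.50, for ICC 0 and 0.05, of 0.778 and 0.617 (10 villages), 0.866 and 0.795 (20), and 0.885 and 0.871 (50).

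**4. Retention, a separate point.** Exactly 90% of 66 and 34 is 59.4 and 30.6. Without any clustering this gives detectable effects of 0.63 and 0.46, and power of 0.76 at the stated effects. In the 66:34 split, 0.60 and 0.44 are reached after rounding only at about 98% retention.

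**The case against.** **The study is exploratory.** Section 9.B.iii says its size rests on timeline and resources and that smaller effects will be estimated, so no sample-size decision depends on the power figure. This stands and lowers the severity. It does not support an unconditional conclusion drawn from an 80% power statement, and under clustering the missed effects may include those of 0.5 SD that the plan says it will capture.

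**The loss may be small.** With 50 villages the 0.5 SD conclusion survives up to an ICC of about 0.27, and with 20 up to about 0.046. This also stands: the size of the loss rests on assumed figures. The ten-village row is the least firm. At ICC 0 its power is 0.81 by formula and 0.78 by simulation, so whether it clears 0.80 depends on the test chosen.

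**The unit of randomisation is not fully settled.** Sections 1 and 12.A contain household-selection wording, Section 12.B has the peer-versus-specialist sentence, and an exact 66/34 split is hard to guarantee when whole villages are assigned. Village randomisation remains the better reading, because Section 12.B states it expressly and gives contamination as the reason. If households were meant, those sections need correcting instead.

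**This is an ethics-board form that refers to a separate research plan.** The analysis may be specified there, and a cross-reference would settle that part. The power figures in this document would still carry no allowance.

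**Conclusion.** The concern holds. The stated 0.60 and 0.44 SD are independent-household figures used for a design described as village-randomised, and nothing else in the documents supplies an allowance. With more than one household per village and a non-negligible ICC, power at those effects is below 80%. The size of the shortfall is unknown without a village count and an ICC. Over the assumed range (10 to 50 villages, ICC 0 to 0.10, no loss to follow-up), the adjusted detectable effect runs from 0.444 to 0.697 SD and power at 0.5 SD from 0.89 down to 0.52. The plan's conclusion therefore holds with many small villages and fails with few. Part of the loss comes from degrees of freedom, but not all: on 98 df, 10 villages at ICC 0.05 still give 0.535 SD. This should be fixed; given the exploratory aim, it does not undermine running the study.

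**What to change.** 1. In Section 9.B.iii, state villages per arm and the expected retained households per village.
2. Compute each detectable effect once from the clustered variance: the independent-household variance times 1 + (m − 1) × ICC, or the sum-of-squares form if village sizes differ. Use noncentral t on about villages − 2 df, less any df used by the planned stratification on peer-led and professional-led zones. Cover an ICC range such as 0 to 0.10 at the assumed retention, with m reduced to match. State that the ICC refers to the baseline-adjusted outcome. Do not rescale the existing 0.60 and 0.44.
3. Delete the concluding sentence or make it conditional on village count and ICC. Keep the statement that smaller effects will be estimated.
4. Name a baseline-adjusted main analysis that accounts for village, and for household where siblings are enrolled, with a small-sample df correction; or name a cluster-level analysis. If the research plan already does this, refer to it.
5. Report the estimated ICC with its confidence interval for the later trial.
6. Reconcile the household-selection wording in Sections 1 and 12.A, and the peer-versus-specialist sentence in 12.B, with village randomisation. If household allocation was intended, correct Sections 2, 12.A and 12.B instead.

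The cost is wording, one recalculation and a village term in the analysis, with no added participants. The stated detectable effect will look less favourable and the intervals will be wider.
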